Appendix 1: Abbreviations and Trademarks**Abbreviations**

ADHF	Acute decompensated heart failure
AE	Adverse Event
AHI	Apnea-hypopnea index
ALT	Alanine transaminase
AST	Aspartate aminotransferase
AUC	Area under the curve
BMI	Body mass index
Ca ²⁺	Calcium
C-CASA	Columbia Classification Algorithm for Suicide Assessment
CHF	Chronic heart failure
CI	Confidence intervals
Cmax	Maximum concentration
CMT2C	Charcot-Marie-Tooth disease Type 2C
CNS	Central nervous system
CO ₂	Carbon dioxide
CONSORT	Consolidated Standards of Reporting Trials
COPD	Chronic obstructive pulmonary disease

CPK	Creatine phosphokinase
CRF	Case report form
CRU	Clinical research unit
CSA	Central sleep apnea
CSR	Cheyne-Strokes respiration
C-SSRS	Columbia Suicide Severity Rating Scale
cTn	Troponin (cardiac)
CTX	Collagen Type I Telopeptide
CV	Cardiovascular
CYP	Cytochrome P450 enzyme
DLco	Diffusing capacity of the lung for carbon monoxide
DLno	Diffusing capacity of the lung for nitric oxide
D _M	Alveolar-capillary membrane conductance
DMPK	Drug Metabolism and Pharmacokinetics
DNA	Deoxyribonucleic acid
DPD	Deoxypyridinoline
E	Epinephrine
ECG	Electrocardiogram
EEG	Electroencephalography
EELV	End expiratory lung volume
EMG	Electromyogram
EOG	Electrooculogram
ER	Emergency Room
FDA	Food and Drug Administration
FEF	Forced expiratory flows
FEV ₁	Forced expiratory volume in 1 second
FOBT	Fecal Occult Blood Test
FRC	Forced residual capacity
FSH	Follicle stimulating hormone
FVC	Forced vital capacity
GCP	Good Clinical Practice
GCSP	Global Clinical Safety and Pharmacovigilance
GSK	GlaxoSmithKline
HBcAb	Hepatitis B core antibody
HbsAg	Hepatitis B surface antigen
HEK	Human embryonic kidney cells
HF	Heart failure
HR	Heart rate
HRT	Hormone Replacement Therapy
IDSL	Integrated Data Standards Library
IEC	Independent ethics committee
IgM	Immunoglobulin
INR	International normalized ratio
IP	Investigational Product
IRB	Institutional review board
IVWRS	Interactive voice web response system

Kg	Kilogram
KO	Knockout
LDH	Lactate dehydrogenase
LFT	Liver function tests
MedDRA	Medical Dictionary for Regulatory Activities
mg	Milligram
mL	Milliliter
MSDS	Material Safety Data Sheet
Na	Sodium
NaCl	Sodium chloride
NE	Norepinephrine
nM	Nanomolar
NO	Nitric oxide
NOAEL	No observed adverse event level
NYHA	New York Heart Association
O ₂	Oxygen
OSA	Obstructive sleep apnea
P1NP	Procollagen type 1 amino-terminal propeptide
PD	Pharmacodynamic
PFT	Pulmonary function tests
P-gp	P-glycoprotein
PGx	Pharmacogenomics
PK	Pharmacokinetics
PTH	Parathyroid hormone
PTS-DMPK	Platform Technologies and Sciences-Drug Metabolism and Pharmacokinetics
QTc	QT interval corrected
QTcB	QT interval corrected according to Bazett's formula
QTcF	QT interval corrected according to Fridericia's formula
RAP	Reporting and analysis plan
RER	Respiratory exchange ratio
RPE	Rating of perceived exertion
SAE	Serious Adverse Event
SDw	Within-subject variability
SOP	Standard Operating Procedure
SRM	Study reference manual
t _{1/2}	Half-life
t _{max}	Time to maximum observed plasma concentration
TRPV4	Transient receptor potential vanilloid 4
µg	Micrograms
ULN	Upper limit of normal
VCO ₂	Volume of carbon dioxide production
Vc	Capillary blood volume
VE	Ventilation
VO ₂	Volume of oxygen
WBC	White blood cells

PREVIOUS TEXT

Appendix 9: Intravenous Saline Infusion

Rapid intravenous saline infusion has been employed to elicit fluid extravasation from the vasculature to the pulmonary interstitium. This methodology has been previously utilized in studies with healthy volunteers [Synder, 2006] and patients with heart failure [Fujimoto, 2013; Robbins, 2014; Andersen, 2015].

Subject Evaluation Prior to Infusion

On Day 5 of both study periods, the subject will be admitted to the clinical research unit (CRU) and undergo routine weight measurement and vital sign assessments including temperature, systolic and diastolic blood pressures, heart rate, respiratory rate, and pulse oximetry to assess O₂ saturation. The subject will also undergo a pulmonary examination.

While in a sitting position, a dyspnea assessment, utilizing a standardized 5-point Likert scale, will be obtained to document the subject's current status. A subject, who is not severely or very severely short of breath, will undergo an orthopnea test (placed supine with head \leq 20 degrees relative to horizontal). After an equilibration period of 2 minutes, the 5-point scale will be repeated. A subject who reports a worse dyspnea score when supine compared to sitting will be categorized as having orthopnea. Subjects categorized with having orthopnea will not be eligible to participate in the saline infusion.

Study treatment will be administered after all planned pre-dose assessments for Day 5 are completed.

Saline Infusion Procedure

A subject, who is judged by the Investigator to be in a stable condition and without obvious congestion, will then undergo the intravenous saline infusion procedure. This procedure will be conducted in the clinical research unit, which is adjacent to the catheterization laboratory, in the presence of a cardiologist and monitoring personnel. A crash cart will be accessible, and intravenous diuretic will be available, if necessary.

An 18-gauge venous catheter will be inserted into a prominent antecubital vein while the subject is semi-recumbent (approximately 45°). The subject will remain in a semi-recumbent position throughout the procedure.

DLco and DLno measurements and simple spirometry assessments will be obtained prior to the initiation of the infusion.

Prewarmed 0.9% normal saline will be infused intravenously at a rate of 150 mL/min to a total volume of 500 mL. During the saline infusion, blood pressure, heart rate, respiratory rate, and O₂ saturation, will be continuously monitored, and any physical symptoms recorded.

DLco and DLno measurements and spirometry assessments will be obtained after the completion of the infusion.

Post-infusion Monitoring

Following the completion of the saline infusion procedure, the subject will remain in the clinical research unit for the next 4 hours. Blood pressure, heart rate, respiratory rate, and O₂ saturation, will be continuously monitored, and any physical symptoms recorded. The subject will also be assessed for dyspnea and orthopnea, as described above, at hourly intervals.

After the 4-hour period, the subject will be eligible to leave the CRU if heart rate and respiratory rate are within 20% of the baseline value, O₂ saturation is within 2% of the baseline value, and if the dyspnea score is the same as the baseline score.

The subject will continue to be monitored by the Preventice BodyGuardian Remote Monitoring System as described in Section 7.4.7 of the protocol; ECG, heart rate, respiratory rate and activity level will be measured continuously.

Any worsening of heart failure that requires treatment in the 48 hours subsequent to the saline infusion will be reported as a serious adverse event.

Individual Stopping Criteria During the Saline Infusion Procedure

If the subject demonstrates one of the following changes during the saline infusion, the infusion should be discontinued:

- Decrease in O₂ saturation of >4% compared to baseline
- Increase in respiratory rate of >20% compared to baseline
- Any increase in dyspnea perceived by the patient

If the subject has met one of these criteria during or immediately after the infusion, the subject should be carefully monitored and given intravenous diuretic treatment, intravenous or sublingual nitrates, or other treatment as required.

The subject may continue in the study. However, if this response occurred in the first study period, the subject should not undergo a second saline infusion in the subsequent study period.

Discontinuation of Saline Infusion Procedure

If during the conduct of the study, two subjects meet the individual stopping criteria during the infusion or demonstrate a worsening of heart failure in the 48 hours after completion of the infusion, this challenge procedure will be removed from the study design. No other subjects will undergo this assessment.

Reporting of Adverse Outcomes Associated with the Saline Infusion

Any of the following outcomes must be reported to the sponsor as a serious adverse event:

- Treatment with intravenous diuretic subsequent to the saline infusion
- Need for continued monitoring in the CRU beyond the 4-hour mandated observation period
- Any worsening of heart failure that requires treatment during the 48-hour monitoring period after the saline infusion procedure

These events will be reported by the investigator as serious adverse events in the InForm electronic data collection tool. They will be reported by the sponsor to the FDA as an Expedited Report via electronic submission in eCTD format to the IND, as a 7-day or 15-day IND safety report, as applicable per timeframe specified in 21 CFR 312.32(c)(1). The completed report will also be provided to the IRB.

REVISED TEXT

Appendix 9: Intravenous Saline Infusion

Rapid intravenous saline infusion has been employed to elicit fluid extravasation from the vasculature to the pulmonary interstitium. This methodology has been previously utilized in studies with healthy volunteers [Synder, 2006] and patients with heart failure [Fujimoto, 2013; Robbins, 2014; Anderson, 2015].

Subject Evaluation Prior to Infusion

On Day 5 of both study periods, the subject will be admitted to the ~~clinical research~~ unit (~~CRU~~) and undergo routine weight measurement and vital sign assessments including temperature, systolic and diastolic blood pressures, heart rate, respiratory rate, and pulse oximetry to assess O₂ saturation. The subject will also undergo a pulmonary examination.

While in a sitting position, a dyspnea assessment, utilizing a standardized 5-point Likert scale, will be obtained to document the subject's current status. A subject who is not severely or very severely short of breath will undergo an orthopnea test (placed supine with head \leq 20 degrees relative to horizontal). After an equilibration period of 2 minutes, the 5-point scale will be repeated. A subject who reports a worse dyspnea score when supine compared to sitting will be categorized as having orthopnea. Subjects categorized ~~with~~ as having orthopnea will not be eligible to participate in the saline infusion.

Study treatment will be administered after all planned pre-dose assessments for Day 5 are completed.

Saline Infusion Procedure

A subject who is judged by the Investigator to be in a stable condition and without obvious congestion will then undergo the intravenous saline infusion procedure. This

procedure will be conducted in the ~~clinical research~~ unit, ~~which is adjacent to the catheterization laboratory~~, in the presence of a cardiologist and monitoring personnel. A crash cart will be accessible, and intravenous diuretic will be available, if necessary.

An 18-gauge venous catheter will be inserted ~~into a prominent antecubital vein~~ while the subject is semi-recumbent (approximately 45°). The subject will remain in a semi-recumbent position throughout the procedure.

DLco and DLno measurements and simple spirometry assessments will be obtained prior to the initiation of the infusion.

Prewarmed 0.9% normal saline will be infused intravenously at a rate of **approximately** 150 mL/min to a total volume of 500 mL. During the saline infusion, blood pressure, heart rate, respiratory rate, and O₂ saturation, will be continuously monitored, and any physical symptoms recorded.

DLco and DLno measurements and spirometry assessments will be obtained after the completion of the infusion. **Additional details are provided in the SRM.**

Post-infusion Monitoring

Following the completion of the saline infusion procedure, the subject will remain in the ~~clinical research~~ unit for the next 4 hours. Blood pressure, heart rate, respiratory rate, and O₂ saturation, will be continuously monitored, and any physical symptoms recorded. The subject will also be assessed for dyspnea and orthopnea, as described above, at hourly intervals.

After the 4-hour period, the subject will be eligible to leave the ~~CRU~~ unit if heart rate and respiratory rate are within 20% of the baseline value, O₂ saturation is within 2% of the baseline value, and if the dyspnea score is the same as the baseline score.

The subject will continue to be monitored by the Preventice BodyGuardian Remote Monitoring System as described in Section 7.4.7 of the protocol; ECG, heart rate, respiratory rate and activity level will be measured continuously.

Any worsening of heart failure that requires treatment in the 48 hours subsequent to the saline infusion will be reported as a serious adverse event.

Individual Stopping Criteria During the Saline Infusion Procedure

If the subject demonstrates one of the following changes during the saline infusion, the infusion should be discontinued:

- Decrease in O₂ saturation of >4% compared to baseline
- Increase in respiratory rate of >20% compared to baseline
- Any increase in dyspnea perceived by the patient

If the subject has met one of these criteria during or immediately after the infusion, the subject should be carefully monitored and given intravenous diuretic treatment, intravenous or sublingual nitrates, or other treatment as required.

The subject may continue in the study. However, if this response occurred in the first study period, the subject should not undergo a second saline infusion in the subsequent study period.

Discontinuation of Saline Infusion Procedure

If during the conduct of the study, **two** subjects meet the individual stopping criteria during the infusion or demonstrate a worsening of heart failure in the 48 hours after completion of the infusion, this challenge procedure will be removed from the study design. No other subjects will undergo this assessment.

Reporting of Adverse Outcomes Associated with the Saline Infusion

Any of the following outcomes must be reported to the sponsor as a serious adverse event:

- Treatment with intravenous diuretic subsequent to the saline infusion
- Need for continued monitoring in the **CRU unit** beyond the 4-hour mandated observation period
- Any worsening of heart failure that requires treatment during the 48-hour monitoring period after the saline infusion procedure

These events will be reported by the investigator as serious adverse events in the InForm electronic data collection tool. They will be reported by the sponsor to the FDA as an Expedited Report via electronic submission in eCTD format to the IND, as a 7-day or 15-day IND safety report, as applicable per timeframe specified in 21 CFR 312.32(c)(1). The completed report will also be provided to the IRB.

12.11. Appendix 11: Country Specific Requirements

No country-specific requirements exist.

1. REPORTING & ANALYSIS PLAN SYNOPSIS

Overview	Key Elements of the RAP
Purpose	
 This RAP details all planned analyses and outputs required for the final Clinical Study Report (CSR) of Study 201881.
Protocol	
 This RAP is based on the protocol amendment 02 (Dated: 19-APR-2016) for Study 201881 [GlaxoSmithKline Document Number: Error! Reference source not found.].
Primary Objective	
 To assess the effect of GSK2798745 on pulmonary gas transfer
Primary Endpoint	
 Change in the diffusing capacity for carbon monoxide (DLco)
Study Design	
 This is a randomized, double-blind, sponsor-unblinded, placebo-controlled, 2X2 crossover study in adults with heart failure. 12 subjects are planned to complete both treatment periods. Additional subjects up to 24 in total maybe needed based on interim decision
Planned Analyses	
 Interim analyses are detailed within Section 4.1 where applicable. All decisions regarding final analysis, as defined in this RAP document, will be made prior to Database Freeze (unblinding) of the study data.
Primary Analysis Population	
 The 'All Subjects' Population is defined as all randomized subjects who receive at least one dose of study medication. The 'Analysis Population' is defined as subjects in the 'All Subjects' population having baseline and post-baseline assessments of the endpoint of interest for both periods. The 'Per Protocol' Population will consist of any 'Analysis Population' subjects who are compliant with protocol-specific criteria. Subjects with specified protocol deviations will be excluded. The 'Pharmacokinetic (PK)' Population is defined as subjects for whom a pharmacokinetic sample was obtained and analysed.
Hypothesis	
 An estimation approach will be used for the comparison between GSK2798745 treatment and placebo for the change from baseline in DLco at Day 4 and Day 7. Point estimates and associated 95% confidence intervals for the differences in means will be constructed to provide a plausible range of values for the true comparisons of interest.
Primary Analyses	
 Profiles for DLco will be summarized and presented graphically by treatment group and visits as appropriate for the data. The change from baseline in DLco at Day 4, Day 6 and Day 7 will be calculated and summarized in tabular format and/or graphically by treatment. For the change from baseline in DLco, a statistical analysis will be performed using a mixed effect model with repeated measures with a fixed effect term for treatment, period and day, with a random effect for subject, and baseline as a covariate, if data permit. Point estimates and associated 95% confidence intervals will be constructed for the differences between the active treatment and placebo.

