9. STATISTICAL CONSIDERATIONS AND DATA ANALYSES

This is a double-blind study with the sponsor un-blinded, which allows data to be reviewed on an on-going basis by the sponsor.

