4. PLANNED ANALYSES

4.1. Interim Analyses

- There will be ongoing data reviews by the study team of the un-blinded safety and pharmacokinetics data throughout the trial progression.
- After approximately 6 Subjects complete both study periods, a sponsor un-blinded interim analysis will be performed on DLco and other variables of potential clinical relevance. The programming code for this interim analysis will be provided by the study statistician.

- After approximately 9 subjects complete both study periods, a sponsor un-blinded interim analysis will be performed.
- After 12 subjects complete both study periods, prior to DBF, a sponsor un-blinded interim analysis will be performed on DLco.

A Bayesian predictive probability of change in DLco with 18 patients will be calculated, and the intra-subject variability will be estimated. These analyses will inform a decision to enrol up to 12 additional subjects.

Given the decision to not continue the TRPV4 HF work on this asset, the Bayesian prediction was performed on 10 subjects and a decision was made to only enrol one more patient. Therefore, an interim analysis will not be performed on 12 subjects.

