4.2. Final Analyses

The final planned analyses will be performed after the completion of the following sequential steps:

1. All subjects have completed the study as defined in the protocol.
2. All required database cleaning activities have completed the final database release and database freeze has been declared by Data Management.
3. All criteria for unblinding the randomisation codes have been met.
4. Randomisation codes have been distributed accordingly to RandAll NG procedures.

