5.1. Protocol Deviations

- Important protocol deviations (including deviations related to study inclusion/exclusion criteria, conduct of the trial, patient management or patient assessment) will be summarised and listed.
- Important deviations which result in exclusion from the analysis population will also be summarised and listed. (Please refer to [Appendix 1: Protocol Deviation Definitions for Per Protocol Population](#)).
- Protocol deviations will be tracked by the study team throughout the conduct of the study in accordance with the Protocol Deviation Management Plan.
 - Data will be reviewed prior to unblinding and freezing the database to ensure all important deviations and deviations which may lead to exclusion from the analysis are captured and categorised on the protocol deviations dataset.
 - This dataset will be the basis for the summaries and listings of protocol deviations.

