8.1.2. Statistical Model

Analysis of variance (ANOVA) with repeated measure will be performed on DLco. The primary interested outcome is to compare the treatment effects of the two treatments, where the treatment effect is defined as the change of DLco at the end of each treatment period from the corresponding baseline. Methodological differences in how DLco is collected at the two site causes variance differences by site so it will not be possible to pool DLco values across sites.

The model assumes no cross-over effect. This assumption will be tested by the following code:

```
data results;
  set results;
  contrast = 0.5*(baseline_period1 - baseline_period2);
run;

proc ttest alpha=0.10;
  class seq;
  var contrast;
run;
```

Due to the small sample size, this test has a low power to detect cross-over effects, so the assumption will also be tested graphically by looking at a plot of measures overtime. If there are any departures from the distributional assumptions, alternative models will be explored using appropriately transformed data.

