11. APPENDICES

Section	Appendix
RAP Section 5 : Analysis Populations	
Section 11.1	Appendix 1 : Protocol Deviation Management and Definitions for Per Protocol Population
RAP Section 6 : General Considerations for Data Analyses & Data Handling Conventions	
Section 11.2	Appendix 2 : Time and Events
Section 11.3	Appendix 3 : Treatment States & Phases
Section 11.4	Appendix 4 : Data Display Standards & Handling Conventions 
 • Study Treatment & Sub-group Display Descriptors • Baseline Definitions & Derivations • Reporting Process & Standards
Section 11.5	Appendix 5 : Derived and Transformed Data 
 • General, Study Population & Safety • Efficacy • Pharmacokinetic • Pharmacodynamic / Biomarkers
Section 11.6	Appendix 6 : Premature Withdrawals & Handling of Missing Data 
 • Handling of Missing Dates • Handling of Partial Dates
Section 11.7	Appendix 7 : Values of Potential Clinical Importance 
 • Laboratory Values • ECG's • Vital Signs
Section 11.8	Appendix 8 : Laboratory A&R Datasets
Section 11.9	Appendix 9 : Biomarker A&R Datasets
Other RAP Appendices	
Section 11.10	Appendix 10 : Abbreviations & Trade Marks
Section 11.13	Appendix 11 : List of Data Displays
Section 0	Appendix 12 : Example Mock Shells for Data Displays

11.1. Appendix 1: Protocol Deviation Definitions for Per Protocol Population**11.1.1. Exclusions from Per Protocol Population**

A subject meeting any of the following criteria will be excluded from the Per Protocol population:

Number	Exclusion Description
01	Subject takes prohibited Concomitant Medications
02	Others as defined in the PDMP

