11.6.2. Handling of Missing Data

Element	Reporting Detail
General	
 Missing data occurs when any requested data is not provided, leading to blank fields on the collection instrument: 
 [1] These data will be indicated by the use of a “blank” in subject listing displays. [2] Answers such as “Not applicable” and “Not evaluable” are not considered to be missing data and should be displayed as such.
Outliers	
 Any subjects excluded from the summaries and/or statistical analyses will be documented along with the reason for exclusion in the clinical study report.

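### The SAP says final-analysis decisions and exclusions precede unblinding, but the sponsor was unblinded throughout while choices reaching the DLco estimate were still open

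*SAP*

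**What the plan says.** **On timing.** The Planned Analyses row of SAP 1 reads: "All decisions regarding final analysis, as defined in this RAP document, will be made prior to Database Freeze (unblinding) of the study data". SAP 5.1 says of the deviation review: "Data will be reviewed prior to unblinding and freezing the database to ensure all important deviations", including those that may lead to exclusion. SAP 4.2 lists the steps to the final analysis. Database freeze comes first, then "All criteria for unblinding the randomisation codes have been met", then distribution of the codes.

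**On who is blinded.** Protocol 9 opens: "This is a double-blind study with the sponsor un-blinded, which allows data to be reviewed on an on-going basis by the sponsor". Protocol 6.3 names the sponsor and the clinical pharmacist as unblinded. Protocol 9.3.2 extends the running review to efficacy, by individual subject and by treatment group, and keeps subjects and site personnel blinded apart from the pharmacist. SAP 4.1 plans sponsor-unblinded interims at about 6, 9 and 12 subjects, naming DLco at 6 and 12. It then reports that "the Bayesian prediction was performed on 10 subjects and a decision was made to only enrol one more patient", and cancels the look at 12.

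**On what is still open.** If distributional assumptions look doubtful, SAP 8.1.2 says "alternative models will be explored using appropriately transformed data". On outliers, SAP 11.6.2 says only: "Any subjects excluded from the summaries and/or statistical analyses will be documented along with the reason for exclusion". SAP 11.4.3 drops visits recorded as out-of-window deviations from the statistical analyses.

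**On the site restriction.** SAP 8.1.2 says DLco cannot be pooled across the two sites, and the programming note to Table 2.04 (SAP 11.13.5) runs the DLco model at one of them. Protocol 9.4.1 has no such restriction. SAP 3.1 declares no change from the protocol's analysis plan.

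**The concern.** Settling the analysis before unblinding protects an estimate only if the people settling it cannot see how each option falls by treatment. Here database freeze is treated as the moment of unblinding, while the people who own the plan have had treatment codes from the start. A study report that repeated the synopsis would describe choices of scale, exclusion or site as made blind when the documents cannot support that.

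The trial is small, so this matters in practice. With about 11 subjects in all, and fewer if the DLco model keeps one site, a single exclusion can move the result noticeably.

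**Working it through.** **1. The statements side by side.**

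| What the SAP implies | What the documents show |
|---|---|
| Decisions precede unblinding (SAP 1) | Sponsor unblinded by design (Protocol 6.3, 9; the SAP 1 study-design row says so too) |
| Exclusion review precedes unblinding (SAP 5.1) | Sponsor may see individual efficacy data and summaries by treatment at any time (Protocol 9.3.2) |
| Codes released after freeze (SAP 4.2) | Prediction already run on 10 subjects (SAP 4.1) |

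SAP 4.1 does not call the prediction at 10 unblinded. That is an inference. It replaced a sponsor-unblinded interim, and Protocol 9.3.2 defines the quantity predicted as a difference between GSK2798745 and placebo, which needs treatment labels. The SAP reports the prediction in the past tense, so the current text was settled after it. If the final set is those 10 plus one, the look covered 10/11 = 91% of subjects.

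No firewall, blinded statistician or independent exclusion review is described.

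**2. The plan's own precision figure.** Inputs from Protocol 9.2: N = 12, SDw = 1.5 for change from baseline, difference 2.3.
- SE = SDw × √(2/N) = 1.5 × √(2/12) = 0.612.
- Half-width = t(0.975, 10 df) × SE = 2.228 × 0.612 = 1.364. The plan says about 1.36.
- Power from the noncentral t is 92.2%. The plan says more than 90%.

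The figures reproduce, so 1.5 is the within-subject SD per period. The SD of one subject's active-minus-placebo difference is 1.5 × √2 = 2.12.

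**3. What one exclusion could do.** Take a subject whose difference lies 2 × 2.12 = 4.24 from the mean. Removing that subject from m moves the mean difference by 4.24/(m − 1). This ignores the period term. The number at the retained site is not given, so m is assumed to be 6 to 10.
- m = 6: 4.24/5 = 0.85, or 37% of 2.3.
- m = 10: 4.24/9 = 0.47, or 20% of 2.3.

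The two-SD subject is an example; no rule in the plan would remove that subject.

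**4. Why the date of the site restriction matters.** Assume no treatment effect, 11 subjects, SDw 1.5 at both sites, and m = 6 to 10 at the retained site. Over 200,000 simulated trials, always taking the more favourable of all 11 and the retained site biases the estimate upward by 0.23 (m = 6) to 0.08 (m = 10). The chance that either 95% interval lies above zero is 4.2% to 3.2%, against 2.5% for one fixed analysis. This is illustration only. The SAP says variances differ by site, and nothing suggests that the choice was made this way.

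**The case against.** **The case for the plan.** Sponsor unblinding is declared openly, in the same synopsis table as the sentence at issue. The study is phase 2a and aims at estimation. Subjects and site staff stay blinded, so the DLco measurements are largely protected. The parenthesis after database freeze can be read as the formal release of codes for the final run. Alternative models are conditional on a failed assumption, SAP 11.6.2 requires a documented reason for any exclusion, and Protocol 9.4 commits to using all available data within the populations. The site restriction has a stated methodological reason.

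Most of this stands, and it means the design itself is not at fault. It does not rescue the assurance. A formal release date says nothing about who already knew the codes. A documented reason is not a criterion set in advance. The condition on alternative models has no trigger or rule.

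**Stronger readings the documents do not support.**
- *Per Protocol exclusions move the DLco result.* The open-ended item "Others as defined in the PDMP" invites this. But SAP 8.1.1 bases efficacy on the Analysis Population, as does Table 2.04, and the only listed Per Protocol table is a pharmacokinetic one (4.02). The deviation management plan is not available, so its criteria may already be fixed.
- *Repeated looks inflate the error rate.* The plan gives intervals without an efficacy stopping boundary. The interim rules concern variance and futility, although Protocol 9.3.2 also lets efficacy inform recruitment. The SAP does not confirm that the looks at about 6 and 9 took place.
- *The SAP was reshaped by results.* The logged amendment removes an exploratory Bayesian analysis and adds disclosure outputs; it records no change to the DLco model or exclusions. The n=10 heading on the EFF_F23 mock shell is an example to be adjusted to the data.

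**Conclusion.** The contradiction is certain, because it rests on the text alone: SAP 1 and 5.1 claim a safeguard that the sponsor-side design does not provide. Three open routes can still reach the DLco estimate: a change of model or scale, subject exclusions without a criterion, and deviation coding that removes visits or subjects. A fourth choice, the one-site restriction, is already in the SAP but is neither dated against the unblinded looks nor declared in SAP 3.1.

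No bias is shown. The size of any shift cannot be fixed without the number of subjects at the retained site. The range of 0.47 to 0.85 rests on an assumed 6 to 10 subjects, on SDw 1.5, and on an arbitrary two-SD subject. The point is worth correcting because the remedy is cheap and the report would otherwise repeat a statement that its own SAP contradicts.

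**What to change.** 1. In SAP 1 and 5.1, replace the wording that puts decisions and exclusions before unblinding with a plain statement that the sponsor was unblinded. In SAP 4.2, say that code release is a formal step only. Give the date of each DLco look and of each analysis decision, including the site restriction, and list that restriction as a change in SAP 3.1.
2. Name one lead DLco analysis: untransformed change from baseline, the Analysis Population, no outlier or discretionary exclusions, and one explicitly named model. The model has to be named because SAP 1 describes a mixed model with a baseline covariate and SAP 8.1.2 a repeated-measures ANOVA. Label every transformation, exclusion or alternative model as a sensitivity analysis.
3. Have existing site staff without treatment codes set the deviation flags and the valid-manoeuvre flags. SAP 11.5.1 gives the second task to a pulmonologist but does not say whether that person is blinded.

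**Cost.** SAP wording, a short dated record and a small amount of sensitivity analysis. The report loses the claim that all decisions preceded unblinding.
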